The specific aims of this pilot project are:

1) To evaluate the feasibility of studying whether implementation of family gardens paired with a nutrition intervention program in rural Guatemala will lead to improvements in maternal and child dietary diversity, child growth and household food insecurity compared to a nutrition intervention program alone.

2) Evaluate the implementation of the intervention through the Reach Effectiveness Adoption Implementation Maintenance (RE-AIM) framework.

We hypothesize that by augmenting a standard nutrition intervention with improved household food access through a garden intervention, child growth, dietary diversity and food security will improve compared to outcomes with the nutrition intervention alone.

2. Background

Children in Guatemala are at high nutritional risk, with a 47% prevalence of stunting (chronic malnutrition) and low full coverage with vitamin A supplements (UNICEF 2016). Only half of Guatemalan children receive a minimum acceptable diet (according to World Health Organization criteria measuring dietary diversity and meal frequency) from 6-23 months (UNICEF 2016). The indigenous Mayan population is disproportionately affected by poverty, food insecurity and malnutrition, with the prevalence of chronic malnutrition reaching as high as 70% in rural areas.

Wuqu' Kawoq/Maya Health Alliance (MHA) has conducted several studies to determine what nutrition interventions really work to prevent and treat chronic malnutrition. As a result of these studies, MHA established a home-based nutrition program whose goal is catch-up growth, improvement of minimum dietary diversity, minimum meal frequency, and minimum acceptable diet and increased caregiver knowledge. In a 50-child pilot, this intervention resulted in a mean change in height for age Z score (HAZ) from -3.67 ± 0.99 to -3.37 ± 0.89 over 6 months and an increase from 15-21% on minimum acceptable diet. In a subsequent RCT of this intervention, a trend toward improved growth at 6 months was observed, although the change was not statistically significant. However, minimum dietary diversity and minimum acceptable diet both improved significantly (risk difference 16.9 and 15.9%, respectively). The intervention also resulted in improved daily intake of legumes, eggs, and vitamin A rich fruits and vegetables (risk difference 16.5, 10.4, 12.7% respectively) (Martinez et al, 2018).

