Agriculture is a major economic activity in Guatemala, with 70% of families working in this sector. Family agriculture has many obstacles, including lack of access to land and the expansion of cash crop (e.g., sugar cane, African palm) plantations. Most of the food that is grown locally is exported, rather than being used for local consumption.

Public and private organizations in Guatemala have worked to promote the production of food for consumption. However, very few of them have measured the impact of agricultural initiatives on nutritional status. Moreover, this is the first study in North Tecpán to evaluate the potential impact that adding a home food production (for

PROTOCOL TITLE:

Evaluating a family-based nutrition and garden intervention in rural Guatemala

consumption) component to a health-oriented nutrition program can have on maternal and child diet quality and nutritional status and household food security.

3. Study Design

This is a quasi-experimental study with an intervention group and a nonrandomly selected control (standard care) group.

- The *standard-of-care group* will consist of subjects recruited from Maya Health Alliance's nutrition program in prioritized communities of *North Tecpán, Chimaltenango, Guatemala*. Subjects in the standard care group will receive the current standard child nutrition care (growth monitoring, deworming medication, micronutrient supplementation, nutrition education classes and home visits).
- The *intervention group* will consist of subjects recruited from MHA's nutrition program in prioritized communities of *San Andrés Semetabaj, Sololá, Guatemala*. Subjects in the intervention group will receive the standard child nutrition care plus an additional agriculture component (agriculture education classes, supplies to build a home garden near the family home and on-going agricultural support).

A quasi-experimental design was selected because it was determined that household level randomization would be culturally and logistically difficult.

Both sites are rural. The intervention and control communities are 90 minutes apart by car and have similar prevalence of chronic malnutrition in children and similar sociodemographic characteristics (education levels, economic activity, health services, school access and food access).

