In addition to the primary study endpoints (defined below), we will use the RE-AIM framework (Glasgow 1999) to evaluate the implementation of the intervention at the caregiver, provider and community levels. Broadly, the five elements of RE-AIM are: reach, effectiveness, adoption, implementation and maintenance. For each element, a variety of factors affecting implementation will be assessed. A select number of constructs from the Consolidated Framework for Implementation Research (CFIR) (Damschroder 2013) will also be considered as implementation factors within the RE-AIM framework. Data for this implementation analysis will be gathered through program documentation and auditing, home visit surveys, focus groups with participants, key informant interviews and semi-structured community interviews. More details about the RE-AIM framework for this study, the implementation factors to be assessed and the instruments for assessing them are outlined in Appendix J.

4. Inclusion and Exclusion Criteria

The study involves enrollment of subjects into an add-on gardening intervention who are already participating in an intensive standard-of-care nutrition intervention by MHA staff. Therefore, clinical staff (community health workers) at MHA who run that nutrition intervention will ascertain initial interest in participation in this study from their clients enrolled in the nutrition intervention. Subjects will be approached in their homes to discuss potential participation in the study.

PROTOCOL TITLE:

Evaluating a family-based nutrition and garden intervention in rural Guatemala

If clients express initial interest, the community health worker will provide that family's contact information to a study nurse, who is trained in human subject's research ethics and is a native speaker of Kaqchikel, the language spoken by the majority of the potential research subjects. This nurse will then conduct a home visit to potential subjects to explain the proposed research activities in more detail. If the family agrees to participate, then the nurse will administer the consent process and enroll them in the study.

Inclusion criteria are:

- Children who are already scheduled to be enrolled in MHA's intensive home-based nutrition program (non-investigational, standard of care) who are 6-24 months of age at the time of enrollment with a height-for-age Z scores of ≤ -2 – Households of children with height-for-age Z scores of ≤ -2.5 will be prioritized.

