- At least one caregiver willing to provide written informed consent
- Caregiver of a child enrolled in the study, including women who may be pregnant
- Planned residence in the study area for the next 18 months

Exclusion criteria are:

- Children with acute malnutrition (weight for length Z scores of ≤ -2.0)
- Children with a severe medical illness that affects growth (e.g., heart disease, kidney disease, genetic condition) as determined by a MHA/Wuqu' Kawoq staff physician.
- Caregivers with cognitive impairments that prevent them from being able to provide informed consent

Children who are ineligible for enrollment in the research study will receive standard care (the home-based nutrition intervention) from MHA.

5. Number of Subjects

The study will enroll 140 children and their primary caregivers into two study groups: standard-of-care (n=70 children and 70 caregivers) and intervention (n=70 children and 70 caregivers).

6. Study Timelines

Five to ten families per month will be enrolled into the study from each study community. We anticipate that recruitment will take ~7-14 months.

The research team will have contact with enrolled participants over the course of 18 months. The primary study data collection time points will be at 0 months (enrollment), 6 months (end of standard of care/nutrition intervention), 12 months, and 18 months. It is anticipated that each of these study data collection visits will last approximately 1 hour,

PROTOCOL TITLE:

Evaluating a family-based nutrition and garden intervention in rural Guatemala

for a total of 4 hours. In addition to that, for the *intervention group only*, data will be collected at the first monthly agricultural home visit and at one additional agricultural home visit approximately 4 months thereafter. Each of these agricultural home visits will last approximately 1 hour for a total of an additional 2 hours. Combined, the total data collection time for the participant in the *intervention* group will be 6 hours.

The duration of the study interactions with the children and their caregivers is as follows:

- Standard child nutrition care (received by both groups) will last 6 months and will include nutrition classes for 5 weeks and one home visit a month. Standard nutrition care will involve approximately 16 hours of contact with MHA clinical personnel.

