- The add-on agricultural/garden intervention (received by the intervention group only) will last 8 months and will include monthly agricultural classes and monthly home visits. The agricultural/garden intervention will involve approximately 16 hours of contact with MHA agricultural personnel, in addition to the time dedicated to the standard nutrition intervention.

A select number of participants (approximately 10) in the *intervention group* only will be asked to participate in one of two focus groups, approximately 90 minutes in length, between 6 and 9 months after the first enrollment. Participation in the focus groups will be fully voluntary and will not have any impact on the services or benefits received by the participants.

A small number of community leaders and Wuqu' Kawoq staff will be asked to participate in interviews, approximately 90 minutes in length, between 6 and 9 months after the first enrollment. Participation in the interviews will be fully voluntary.

The expected total duration of the study is approximately 3 years from the date of IRB approval.

7. Study Endpoints

The primary endpoints of this study are changes in the prevalence of:

- *Adequate diet quality*, as assessed by the World Health Organization (WHO) Infant and Young Child Feeding Indicators (IYCFI) (WHO, 2007) minimum dietary diversity, minimum meal frequency, minimum acceptable diet) for children and the Minimum Dietary Diversity for Women (MDD-W) indicator for caregivers. (FAO 2016)
- *Household food insecurity*, as assessed by the Global Food Insecurity Experience Scale (household referenced) (FAO 2017)

Secondary endpoints of the study include changes in: child length-for-age Z-score; child weight-for-age Z-score; child weight-for-length Z-score; child prevalence of stunting, wasting and underweight; and household total crop species diversity.

PROTOCOL TITLE:

Evaluating a family-based nutrition and garden intervention in rural Guatemala

This study involved no more than minimal risk, so no safety endpoints are specified.

8. Research Setting

The study will be conducted in prioritized communities of North Tecpán, Chimaltenango and San Andrés Semetabaj, Sololá (see additional details in **Section 3. Study Design**). These are rural Mayan language speaking communities where MHA has been working providing primary care and nutrition services for several years. MHA collaborates closely with multiple other NGOs as well as Ministry of Health staff in the region.

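### Eligibility fixes baseline stunting near 100% and wasting near 0%, so their change in prevalence is an unadjusted follow-up difference between two non-randomised sites

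*Combined protocol and SAP*

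**What the plan says.** Section 7 (Study Endpoints) gives the growth outcomes as changes: "Secondary endpoints of the study include changes in: child length-for-age Z-score", the other two Z-scores, and "child prevalence of stunting, wasting and underweight".

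Section 4 (Inclusion and Exclusion Criteria) admits children "with a height-for-age Z scores of ≤ -2", adds that "Households of children with height-for-age Z scores of ≤ -2.5 will be prioritized", and excludes "Children with acute malnutrition (weight for length Z scores of ≤ -2.0").

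Section 3 (Study Design) takes each group from one non-randomly chosen area and says that the areas "have similar prevalence of chronic malnutrition in children".

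Section 13 (Data Analysis) names the chi-square test, paired t-tests or a non-parametric substitute, and linear or logistic regression where suitable. It names no covariate and no baseline term for any outcome. It also says that the pilot should yield a first effect size for later studies.

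Growth is part of the stated hypothesis that "child growth, dietary diversity and food security will improve compared to outcomes with the nutrition intervention alone". Section 2 (Background) reports, from an earlier 50-child pilot, a "mean change in height for age Z score (HAZ) from -3.67 ± 0.99 to -3.37 ± 0.89 over 6 months".

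**The concern.** A change in prevalence is normally chosen so that each group is compared with its own starting point. Here the eligibility rule has already set that starting point to the same value in both groups. Subtracting it removes nothing, although the endpoint looks baseline-corrected. A site whose children enter just below -2 will show more recovery than one whose children enter at -3.5, with or without gardens, and the baseline prevalence cannot reveal the imbalance.

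Within a group the direction is also fixed: stunting can only fall from 100% and wasting can only rise from 0%. Either movement could be misread as benefit or harm.

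A distorted growth effect would carry forward into the planning of later studies.

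**Working it through.** The plan states no alpha, power or effect size, so there is no figure of its own to reproduce. Below, alpha is assumed to be two-sided 5%, with 70 children per group (Section 5) and no garden effect.

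**1. The identity.** Let p be the follow-up prevalence in the intervention (I) or control (C) group.
- Stunting: (p_I - 1) - (p_C - 1) = p_I - p_C.
- Wasting: (p_I - 0) - (p_C - 0) = p_I - p_C.

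This needs only the -2 cut-offs. It holds approximately, because a child at exactly -2 is a boundary case and the month-0 reading may differ from the screening value. Eligibility sets no weight-for-age limit, so underweight does vary at baseline.

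**2. How large a gap prioritisation alone could create.** Take the pilot's entry values (mean -3.67, SD 0.99) as a normal source population, cut at -2.
- P(Z ≤ -2) = Φ(1.687) = 0.954 and P(Z ≤ -2.5) = Φ(1.182) = 0.881.
- Share of eligible children at -2.5 or below with no prioritisation: 0.881 / 0.954 = 0.924.
- Mean Z is -3.89 in that stratum and -2.28 between -2.5 and -2, a difference of 1.61.
- The extreme case is one site unprioritised (92%) and the other fully prioritised (100%). The entry gap is (1 - 0.924) × 1.61 = 0.12 Z, or 0.13 Z if the share is rounded to 92%.

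**3. Effect on the stunting comparison at 6 months.** Follow-up Z = -3.37 + b × (entry Z + 3.67) + error, with b = r × 0.89/0.99 and error SD = 0.89 × √(1 - r²). The correlation r is not in the documents and is assumed to be 0.6 to 0.9. Recovery means follow-up Z above -2. Chi-square (no continuity correction) is by exact enumeration.

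| r | b | Recovered, 92% site | Recovered, 100% site | Difference (points) | Chi-square rejects | Rejects if entry equal |
|---|---|---|---|---|---|---|
| 0.60 | 0.54 | 4.7% | 3.5% | 1.2 | 5.9% | 4.7% |
| 0.75 | 0.67 | 4.0% | 2.4% | 1.6 | 7.0% | 4.6% |
| 0.90 | 0.81 | 3.0% | 1.0% | 2.0 | 8.1% | 4.1% |

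Events are few. With equal entry at 92%, about 2 to 3 of 70 per group recover, and at least one group has no recoveries in 7% to 23% of studies.

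**4. What larger effects would need.** If the sites' source populations are assumed to differ, with the same follow-up line, entry gaps of 0.20, 0.38 and 0.68 Z give spurious differences of 1.1 to 1.3, 2.3 to 2.7 and 4.7 to 5.8 points. Chi-square then rejects in about 6% to 6.5%, 7% to 10% and 20% to 31% of studies. The documents supply none of these gaps.

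**5. Does baseline adjustment help?** Assume source means 0.37 Z apart (-3.855 and -3.485), which gives an entry gap of about 0.30 Z, with r from 0.6 to 0.9.

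| Spurious estimate, milder minus more severe site | Both sites share one regression line | Each site regresses to its own mean |
|---|---|---|
| Recovery, log odds ratio, unadjusted | about 0.35 to 0.55 | about 0.8 |
| Recovery, log odds ratio, adjusted for baseline Z | about 0 | about 0.33 to 0.5 |
| Z-score, ANCOVA | about 0 | 0.07 to 0.17 |
| Z-score, raw change | -0.06 to -0.14 | 0.01 to 0.03 |

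For the binary outcome, adjustment is better in both settings, though incomplete in the second. For the continuous Z-score, neither ANCOVA nor raw change is better in both.

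**The case against.** The strongest reply is that little is shown to be wrong. Section 3 reports similar prevalence of chronic malnutrition, Section 13 allows regression, and these are secondary endpoints of a study that calls itself a pilot. Most of this stands, and it limits the size of the point. It does not remove the identity. Similar community prevalence concerns the share below a cut-off, not how far below it the enrolled children lie. An unadjusted chi-square would comply with Section 13 as fully as an adjusted model.

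A reader might infer more than the documents support in three ways.

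- **That uneven prioritisation could produce a large imbalance, such as 70% v 90% at -2.5 or below.** At the pilot's values about 92% are there already, and prioritisation can only raise that share. Such splits need a different source population at one or both sites, which the documents do not describe.
- **That raw change in Z is wrong and ANCOVA right.** That depends on both sites sharing one regression line. If each regresses to its own mean, ANCOVA is the more biased of the two. The fall in SD from 0.99 to 0.89 in 50 children does not settle it: a Pitman-Morgan test gives p = 0.36, 0.27 and 0.10 at assumed correlations of 0.6, 0.75 and 0.9.
- **That the pilot's figures describe the whole study.** They cover 6 months only. Months 12 and 18 are not covered, and no weight-for-length values are given from which to size the wasting comparison.

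**Conclusion.** The point holds for stunting and wasting. Under the conventional cut-offs, their change in prevalence is an unadjusted follow-up difference between two non-randomised sites and corrects for no difference in entry severity. Underweight is outside it.

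The demonstrable size is small: 1 to 2 percentage points and rejection in about 6% to 8% of studies at month 6, in the most that prioritisation alone could do at pilot values. This rests on a normal source population, a linear follow-up model and an assumed correlation of 0.6 to 0.9. Anything larger rests on an assumed site difference, and none is documented. The identity itself needs only the cut-offs.

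The consequence is a possibly distorted secondary effect size. A reader might go on to doubt the primary result, but the primary endpoints are diet quality and food insecurity, which this does not touch.

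**What to change.** In Sections 7 and 13:

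1. State the cut-offs, and define the two outcomes as follow-up status at each visit: recovery from stunting, and incident wasting.
2. Compare groups by logistic regression with continuous baseline length-for-age Z (stunting) or weight-for-length Z (wasting) as covariate, in place of the unadjusted chi-square. If events are few, use a penalised fit, or give counts with exact intervals.
3. Report baseline Z by site, and say that within-group falls in stunting or rises in wasting will not be read as benefit or harm.
4. For the continuous Z-scores, report the baseline-adjusted (ANCOVA) and raw-change estimates side by side without ranking them, and treat disagreement as unresolved site confounding.
5. State the limit: adjustment reduces confounding by measured entry severity and leaves other site differences in place.

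The cost is wording and a little extra analysis. Weight and length are already measured at month 0, so no new data or visits are needed.

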MHA has a dedicated research office located in Tecpán, close to the study communities. The office has dedicated file storage cabinets for research documents, high-velocity internet, dedicated full-disc encrypted phones and computers, statistical software (STATA), and

PROTOCOL TITLE:

Evaluating a family-based nutrition and garden intervention in rural Guatemala

online HIPAA-compliant file servers and a REDcap server. The study budget includes the purchase of a new vehicle for use by the study team. An IT technician and comptroller will provide support to the project as needed.

MHA will provide usual care for treatment of severe medical illness identified during the screening/recruitment phase.

10. Prior Approvals

The protocol is approved by the MHA IRB.

11. Multi-Site Research

N/A – this is not a multi-site study

12. Study Procedures

This study will be conducted in two different sites. These are rural, Mayan language-speaking areas where MHA has been working for several years to provide primary care and child nutrition services.

This is a quasi-experimental study with an intervention group and a non-randomly selected control (standard-of-care) group.

The *standard-of-care group* will consist of subjects recruited from Maya Health Alliance's nutrition program in prioritized communities of *North Tecpán, Chimaltenango*.

The standard-of-care child nutrition services include:

- Intake visit with research nurse to assess basic health history, demographics, WHO IYCFI, FIES and MDD-W for women
- Monthly growth monitoring
- Monthly micronutrient supplementation
- Deworming medication (every 6 months)
- Monthly home visits by community health worker (CHW) to provide individualized growth assessment to mothers
- Nutrition education classes with CHW (nutrition during pregnancy, breastfeeding, complementary feeding, chronic and acute malnutrition, hygiene and nutritious recipes)

The *intervention group* will consist of subjects recruited from MHA's nutrition program in prioritized communities of San Andrés Semetabaj, Sololá. The intervention group will receive all standard-of-care child nutrition services as described above, plus:

- Agriculture education classes with the study agronomist (home garden package, assessment of plant production, weed and pest control, water access, etc.)
- Home garden supplies including seeds and/or seedlings
- Monthly home visits from a study agronomist to provide assistance to build a garden near the family home and on-going support throughout the study

PROTOCOL TITLE:

Evaluating a family-based nutrition and garden intervention in rural Guatemala

Study data will be independently collected by a study nurse for all enrolled subjects at 0, 6, 12 and 18 months:

- Basic health history and demographics Appendix A
- Child weight and length/height Appendix B
- Household Quick Poverty Score (QPS) Appendix C
- Food Insecurity Experience Scale (household) Appendix D
- WHO Infant and Young Child Feeding indicators (child) Appendix E
- MDD-W Indicators (caregiver) Appendix F
- Agriculture Inventory Survey (household) to measure crop diversity and crop utilization Appendix G

Note that child weight and length and WHO IYCFI are already routinely collected as part of evaluation data for the standard-of-care nutrition services.

Additional data will be collected by the study agronomist for the *intervention group only* during the first agricultural home visit and at one additional agricultural home visit approximately 4 months thereafter:

- Agricultural Home Visit Baseline Survey (Baseline Agricultural Practices; Gardening Experience and Motivation) Appendix H
- Agricultural Home Visit Follow-up Survey (Adoption of Methods; Level of Home Garden Maintenance; Hours Worked in Home Garden) Appendix I

13. Data Analysis

Descriptive statistics for each group will be calculated using Stata (StataCorp, College Station, Texas). Family poverty scores will be calculated with a validated numerical scoring system commonly used in Guatemala. Changes in primary and secondary study outcomes will be compared between study groups using the chi-square test, paired t-tests (or the non-parametric equivalent) and linear and logistic regression as appropriate.

Within the intervention group, the rate of overall adoption will be compared descriptively across various demographic groups, and changes in primary and secondary outcomes will also be compared descriptively between adopters and non-adopters. Focus groups and interviews will be coded and analyzed thematically using select constructs from the Consolidated Framework for Implementation Research (CFIR) as a framework.

This is a pilot study to determine the feasibility of a garden intervention and to generate an initial effect size estimate for future, well-controlled studies. As such no formal power analysis will be performed.

14. Provisions to Monitor the Data to Ensure the Safety of Subjects

N/A – this study poses no more than minimal risk

15. Withdrawal of Subjects

There are no safety/stopping rules, so we do not anticipate any withdrawal from the study unless requested by the participant, or in the case that a participant moves out of the study area.

PROTOCOL TITLE:

Evaluating a family-based nutrition and garden intervention in rural Guatemala

Subjects can withdraw from the study at any time that they request. If subjects withdraw from the study, we will retain any existing collected data for analysis, as outlined in the consent form, unless the subjects specifically request otherwise.

If subjects wish to withdraw from the nutrition care services or the agricultural intervention, we will endeavor to continue data collection at the specified timepoints, if they are agreeable.

16. Data Management/Confidentiality

Data sharing between the Academy of Nutrition and Dietetics and UNM is covered under contract FP5579 (effective date 8/1/2018). Per this agreement, all data shared with UNM for this study will be de-identified and transferred using the secure transfer portal provided by UNM HSC Central IT. An account will be created for the contact at AND to login to the portal web site (<https://securetransfer1.health.unm.edu>). Data transfer via this link is protected with Secure Sockets Layer (SSL) capabilities/128-bit encryption. After the transfer, [name] will be granted access to the files transferred by the AND contact via the UNM HSC secure network storage.

All data transfer from MHA to AND, and from AND to MHA, will also occur using a secure transfer portal provided by AND. Data transfer via this portal is protected with Secure Sockets Layer (SSL) capabilities/128-bit encryption.

Research data and unique subject study IDs will be either captured on paper forms or directly entered into MHA's secure Redcap server interface using full-disc encrypted study Android phones or laptop computers (demographics, anthropometrics, quick poverty score, WHO IYCF indicators, MDD-W, crop diversity survey and the additional agricultural data to be collected by the study agronomist) or the Academy of Nutrition and Dietetics Health Informatics Infrastructure (ANDHII) database (WHO IYCF indicators, MDD-W). Both databases are HIPAA-compliant and secure. Study personnel will each be assigned a unique username and password to the Redcap and ANDHII interface. Only PIs or PI's delegated research coordinator will be able to administer user accounts.

If data is captured on paper forms, it will be stored in a locked filing cabinet in MHA's central office, in a location distinct from consent forms.

For study data captured on paper forms, double entry in REDCap will be employed. Bimonthly data quality checks of paper forms and the study databases will be done by the research study coordinator. Native data field definition functions in Redcap and ANDHII will be used to ensure data quality at point of entry by research staff. During bimonthly database checks, any issues identified will be checked manually against an existing original paper forms if possible.

Study personnel will be trained to collect anthropometric and dietary diversity data using standard methods by a supervising study coordinator. All anthropometric measurements will be completed in triplicate during each study visit. Weight will be measured to the nearest 0.1 kg with the use of a Seca 310 hanging scale (Seca, Hamburg, Germany), and length/height will be measured to the nearest 0.1 cm with the use of a portable length board locally constructed according to UNICEF specifications. For data analysis, we will use the mean of the first two readings if they did not differ more than a pre-specified tolerance limit (length/height < 0.5 cm, weight < 0.2 kg). If they differed more than these pre-specified tolerance limits, the third measurement will be compared

PROTOCOL TITLE:

Evaluating a family-based nutrition and garden intervention in rural Guatemala

with the first and second measurements and the pair of measurements that has the smallest difference will be used to calculate the mean.

On-going quality control via data review and random audits of in-field operations (recruitment, anthropometric techniques, dietary diversity, and exit visits) will be performed by the study coordinator. The auditor will perform a triplicate of height and weight measurements of the children and compare results to the measures obtained by the study nurse, at the same time evaluating the measuring technique. The auditor also will perform an independent dietary diversity interview with the children's caregiver, and compare results with the data obtained by the nurse or CHW. Timely feedback will be provided to the study staff as required. Study staff will also participate in monthly anthropometry standardization exercises during which the technique, precision, and reliability of their measurements will be evaluated and reinforced.

At enrollment in the study by the research nurse, each subject will be assigned a unique subject study ID number. This number will be registered on the paper consent form (stored in a locked file cabinet) and in an electronic study spreadsheet, hosted on MHA's HIPAA-compliant in-house file server. This will be the only link between identifiable subject information and their research data. Only the PIs or their delegated research coordinator will have access to this spreadsheet. Control of access to MHA's file server will be directly managed by the MHA PI ([name]) or a delegated research coordinator at MHA.

Identifiable data (consent forms, master lists linking subjects to study ID, birthdates) will be maintained through publication of primary study reports and manuscripts, and for an additional period of 5 years. In addition, fully deidentified data sets will be deposited in public data repositories at the time of report/manuscript publication. No identifiable data will be released at any point.

17. Data and Specimen Banking

No specimens will be collected during the study.

Identifiable data (master lists linking subjects to study ID, birthdates) collected during the study will be stored in secure, electronic databases (See Section 16.13). Consent forms will be stored in a locked filing cabinet in the MHA office in Guatemala. Identifiable data will be maintained through publication of primary study reports and manuscripts, and for an additional period of 5 years. In addition, fully deidentified data sets will be deposited in public data repositories at the time of report/manuscript publication. No identifiable data will be released at any point.

18. Risks to Subjects

The study procedures and activities are not more than minimal risk. The child nutrition services and many of the data collection procedures are part current standard of care at MHA. We do not, therefore, anticipate any adverse outcomes from these procedures and activities.

It is more likely, however, that a caregiver or community member might erroneously ascribe an adverse outcome to the trial. For example, this might occur if a child dies from pneumonia while in the trial, even though this would not be expected to be related to the trial itself. We will address this issue in the following way: The case would be reported by the study nurse and study coordinator to MHA PI [name] and MHA's medical director [name]. [name] will independently adjudicate the event and make a determination on the need for follow-up care. [name] will report the event to MHA's IRB Chair, [name], for independent review, and will

PROTOCOL TITLE:

Evaluating a family-based nutrition and garden intervention in rural Guatemala

also include the event in a study adverse event log, which will be updated weekly and included in each continuing review of the project.

Additionally, we will attempt to minimize conflated adverse outcomes, by excluding all children with acute malnutrition or serious medical illness from the trial as outlined in **Section 4. Inclusion and Exclusion Criteria**. Any child with acute malnutrition or serious medical illness will be immediately referred to the MHA clinical team and will receive comprehensive clinical care.

Another potential risk from the study is that it might cause conflict between the study communities. This could occur because caregivers receiving the nutrition intervention might learn that others are also receiving the additional garden component. We attempt to minimize this risk by recruiting the intervention families from a different community than we recruit the standard-of-care families.

Finally, there is the potential of accidental disclosure of protected health information. Please see **Section 16. Data Management/Confidentiality** for procedures to minimize this risk.

19. Potential Benefits to Subjects

Individuals in both groups may benefit directly. Both groups will receive micronutrient supplementation, deworming medication, home visits and nutrition education, which we anticipate will have positive outcomes on diet quality, catch-up growth, decreased rates of severe stunting, and promotion of cognitive and motor development.

The agriculture intervention group will receive supplies to build a garden, home visits and agricultural education. We anticipate that this will increase their knowledge as well as food availability for their family, even after the study has finished (as the families will keep their garden supplies).

Over the long term, reversing the ill effects of stunting and food insecurity also contributes to improved school performance, adult earning potential, and reduced incidence of adult non-communicable diseases.

This study will help to fill an identified gap in research at the nexus of nutrition, food production and health. Specifically, this work will provide evidence about measurement and indicators used to evaluate diet quality, health impacts and food security when providing nutrition interventions paired with agriculture interventions in rural communities in the highlands of Guatemala.

The implementation evaluation component of this study will provide new knowledge about how various caregiver, provider and community-level factors can affect the implementation of a home gardens program for malnutrition, giving valuable insights into how and why the intervention achieved the level of success that it did.

In this way, the study will help create a functional integrated nutrition and agriculture model that can be used by other organizations who are working or want to work in the treatment and prevention of malnutrition, while offering an understanding of the implementation challenges that

PROTOCOL TITLE:

Evaluating a family-based nutrition and garden intervention in rural Guatemala

they would be likely to confront in the process. Thus, the benefits could conceivably multiply to many more children and their families in Guatemala than simply the study families.

20. Recruitment Methods

Potential subjects will already be planning to participate in MHA's individualized nutrition services in communities surrounding Tecpán, Guatemala (see **Section 4. Inclusion and Exclusion Criteria**).

Subjects (primary caregivers of children participating in the nutrition services) will be approached in their homes during a regular home visit by the community health worker, who will provide initial information about the study. If the subject expresses interest, then the community health worker will provide that person's information to a study nurse, who is trained in human subject's research protocols and a native speaker of Kaqchikel, the language spoken by most of the potential research subjects. This nurse will then conduct a home visit to potential subjects to explain the proposed research activities in more detail.

If more than one child in the home is already enrolled in the MHA nutrition intervention, then only the youngest of those children in the eligible age range will be enrolled in this study.

21. Provisions to Protect the Privacy Interests of Subjects

Subjects will be approached at a time that is most convenient to them, in their homes. We have learned from our previous work in these communities that the best times to conduct home visits are from 8:30 to 11:30 AM or from 2:00 to 4:00 PM.

Study personnel will introduce themselves and ask permission to enter a home before discussing the study, obtaining consent, conducting any surveys or taking anthropometric measurements.

Study personnel will be natively fluent in Spanish and the locally spoken language, or use an interpreter, to ensure comprehension for participants.

Study personnel will not participate in the nutrition services, and therefore will not have access to MHA electronic medical record data.

22. Economic Burden to Subjects

Research Procedures	Number of Samples/Procedures	Responsible Party	
		Study	3rd Party Payer or Participant
Quick poverty score	4	X	
Agriculture Inventory Survey	4	X	

PROTOCOL TITLE:

Evaluating a family-based nutrition and garden intervention in rural Guatemala

